7.1.2. Clinical Investigation Plan (CIP) Deviations

All enrolled subjects will be analyzed and reported based on evaluable data. Major and minor protocol deviations will be tabulated.

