7.1.3. Analysis Set

All safety and effectiveness analyses will be performed on all enrolled subjects, according to the intention-to-treat (ITT) principle. The subject will be considered enrolled after arterial access is achieved and the Valiant Mona LSA Thoracic Stent Graft System has been introduced into the vasculature.

VML_Eval Statistical Analysis Plan **Form** Medtronic Revision [6.0] Page 14 of 27

General Methodology

Data collected from the clinical study will be analyzed as specified in the following sub-sections. Subject data listings, tabular, and graphical representations will be provided. In general, for categorical variables, frequency and percentage will be presented as descriptive statistics. For continuous variables, number of observations, mean, standard deviation, median, minimum, and maximum will be reported.

All key study endpoints will be presented with the point estimate and the corresponding 2-sided 95% confidence interval. Confidence intervals will be included in the final clinical study report, but may not be included in other reports, such as annual progress reports.

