7.4. Handling of Missing, Unused, and Spurious Data and **Dropouts**

In general, imputation of missing data will not be performed for all analyses. However, in cases where the date of adverse event onset is incomplete, the 15th day of the known month or July 1st of the known year will be used unless that results in a date earlier than the date of index procedure, in which case the date of index procedure will be used. For study endpoints, missing data will be listed with subject numbers for review. The imputed AE onset date cannot be later than last known date in the study. For instances where the AE onset date is imputed after the last known date in the study, the last known date in the study will be used for the AE onset date.

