7.9.2. Primary Effectiveness Observation

The primary effectiveness observation is Treatment Success that is defined as successful delivery and deployment of the stent graft (deployment of the Valiant Mona LSA Thoracic Stent Graft System in the planned location with no unintentional coverage of other vessels, assessed intra-operatively, and the removal of the delivery system) and successful exclusion of the aneurysm while maintaining patency of the MSG and BSG at the 30 day visit. Descriptive statistics (frequency and percentage) will be calculated for the primary effectiveness endpoint. A two-sided 95% confidence interval will also be calculated using the exact binomial method.

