7.9.3.3. Exclusion of Thoracic Lesions

Rate of exclusion of thoracic lesions will be reported for 1-month, 6-month and each annual follow-up. The endpoints may be analyzed using site-reported imaging assessments or core lab reported imaging assessments, separately.

Revision [6.0]

Page 21 of 27

Exclusion of Aneurysm

Exclusion of Aneurysm is defined as the absence of a type I or III endoleak associated with the absence of growth of > 5 mm of the maximum measurable aneurysm diameter; reference diameter is the diameter measured at first post-operative imaging exam.

Rate of Exclusion of Aneurysm will be calculated for each scheduled follow-up and the calculation will be based on the number of subjects who had the event divided by number of implanted subjects that are evaluated for that event at the time point. Imaging endpoint analysis time windows will be used to determine if an image assessment belongs to a respective time point. The reporting details can be found in Section 7.2.3 (Table 1).

The endpoint will be derived as follows:

- Subjects having a Type I or III endoleak or having aneurysm growth > 5mm will be considered as failures of the endpoint [defined as k].
- Otherwise subjects without a failure event and having evaluable imaging for both endoleak and aneurysm growth will be considered as a success (i.e. Exclusion of the aneurysm) [defind as m].
- Subjects without a type I or III endoleak and without aneurysm growth > 5mm, but missing one or both imaging assessments will be excluded from the analysis.

The rate will be calculated as m/(m+k), where the numerator will consist of all subjects having success for exclusion of the aneurysm [m]. The denominator will consist of all subjects having exclusion [m] or subjects having a failure event [k].

[figure not shown]
The endoleak component will be derived according to Section 7.9.3.5.

The aneurysm growth component is based on the calculated difference between the assessments at follow-up minus the first post-operative assessment. Subjects must have the maximum aneurysm diameter reported at both the post-operative assessment and the follow-up assessment. If the subject is missing either the post-operative and/or follow-up assessment, the subject is considered to have missing data for this component. The post-operative image can be either at 1 month follow-up or discharge. At each follow-up the largest aneurysm diameter will be used in the calculation of aneurysm diameter change from baseline.

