Scenarios for each possible combination of the component outcomes and the final endpoint assessment of success vs. failure are presented in Table 4. Since the exclusion of aneurysm is an assessment of success with two component events, if both component events are 'success' then the final composite endpoint will be 'success' (scenario 1); if at least one component event is 'failure' then the final composite endpoint is 'failure' (scenario 2,3,4,5 8); if one component event is success, but the other component event is missing due to unevaluable data, the final composite endpoint will be missing

Revision [6.0]

Page 22 of 27

(scenario 6,7); finally, if both components are missing then composite endpoint will be missing (scenario 9):

Table 4. Exclusion of Thoracic Lesion Scenarios

	1 st component	2 nd component even	Composite		
Scenarios	Absence of Type I or III Endoleak	1 st post-operative assessment of Maximum aneurysm/dissectio n/PAU diameter	assessment of Maximum aneurysm/dissection /PAU diameter at each scheduled visit	Absence of growth > 5 mm	endpoint of Exclusion of TAA/PAU
1	Success	evaluable	evaluable	Success	Success
2	Success	evaluable	evaluable	Failure	Failure
3	Failure	evaluable	evaluable	Success	Failure
4	Failure	evaluable	evaluable	Failure	Failure
5	Missing	evaluable	evaluable	Failure	Failure
6	Missing	evaluable	evaluable	Success	Missing
7	Success	Missing/evaluable	Evaluable/missing	Missing	Missing
8	Failure	Missing/evaluable	Evaluable/missing	Missing	Failure
9	Missing	Missing/evaluable	Evaluable/missing	Missing	Missing

Exclusion of Penetrating Aortic Ulcer (PAU)

Exclusion of penetrating aortic ulcer (PAU) is defined as the absence of a type I or III endoleak associated to the absence of growth > 5 mm of the maximum measurable aortic diameter at the level of PAU; the reference diameter is the diameter measured at the first post-operative imaging exam.

The rate of the exclusion of PAU will be calculated similarly to that of the exclusion of Aneurysm;

Exclusion of False Lumen (dissection)

Exclusion of false lumen (dissection) is defined as the exclusion of primary entry tear of dissection associated to the thrombosis of false lumen at the level of stent graft.

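### SAP 7.9.2 leaves the treatment-success denominator open, and the SAP's general rules lead to an evaluable-only rate that omits some early deaths and conversions

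*SAP*

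**What the plan says.** Treatment success (SAP 4.3.2 and 7.9.2) needs technical success in the operating room, then exclusion of the lesion and patency of both stent grafts at the 30-day visit. For its analysis, 7.9.2 says "Descriptive statistics (frequency and percentage) will be calculated for the primary effectiveness endpoint" and adds an exact binomial interval. It names no denominator, gives no rule for a subject who never reaches the 30-day assessment, and refers to no other section.

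The general sections say:

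- 7.1.3: "All safety and effectiveness analyses will be performed on all enrolled subjects, according to the intention-to-treat (ITT) principle". Enrolment is counted from introduction of the device.
- 7.1.2: "All enrolled subjects will be analyzed and reported based on evaluable data".
- 7.4: "In general, imputation of missing data will not be performed for all analyses", and "For study endpoints, missing data will be listed with subject numbers for review".

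The only worked rule for exclusion is in 7.9.3.3, among the additional observations. A recorded type I or III endoleak, or growth above 5 mm, is a failure. Subjects with neither, "but missing one or both imaging assessments will be excluded from the analysis". Table 4 sets this out: scenarios 6, 7 and 9 return a missing result, while scenarios 5 and 8 keep an observed failure even when the other component is missing.

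**The concern.** A 30-day imaging outcome cannot be observed in a subject who dies or is converted first. If that subject had a technically successful implant and no recorded failure, the rate depends on a choice that 7.9.2 does not make. On an all-enrolled denominator the subject stays in and has not been shown to meet the definition. On an evaluable-only denominator the subject disappears, and a poor early course does not lower the success rate.

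This is the primary effectiveness observation of a single-arm study. SAP 4.2 says the data may support marketing applications, and 4.1 ties the dissection subjects to a future premarket approval analysis. There is no control arm in which the same choice would partly cancel. SAP section 3 also describes the methods as flexible, so the denominator could be settled after the data are seen.

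**Working it through.** **Where the rules lead.** Take an enrolled subject with successful deployment who dies or is converted before any evaluable image in the 1-month window, with no recorded failure.

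| Rule | Handling of this subject |
|---|---|
| 7.1.3, all enrolled, ITT | In the denominator; success not shown |
| 7.1.2 with 7.4, evaluable data, no imputation | Not evaluable, so left out |
| 7.9.3.3, Table 4 scenario 9 | Missing, so left out |
| 7.9.3.1, clinical events | A subject with the event by the cutoff stays in; not written for treatment success |
| 7.9.2 | Silent |

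The second and third rows agree, so a programmer looking for a rule would most naturally produce an evaluable-only rate.

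**Inputs.** N = 44 is the planned maximum (SAP section 6). The interval is exact binomial (7.9.2). The documents give no event counts, so these are assumptions:

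- f = known failures, 0 to 4.
- d = early deaths or conversions of the kind described, 1 or 2.

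The plan has no figure of its own to reproduce, because section 6 gives no sample size calculation.

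**Formula.** Successes x = N − f − d. The evaluable-only rate is x/(N − d). The all-enrolled rate, with these subjects not successful, is x/N. The gap is x·d / [N(N − d)]. For f = 2 and d = 1, x = 41 and the gap is 41/(44 × 43) = 2.17 points.

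| f | d | Evaluable-only (95% CI) | All enrolled (95% CI) | Gap, points |
|---|---|---|---|---|
| 0 | 1 | 43/43 = 100.0% (91.8–100.0) | 43/44 = 97.7% (88.0–99.9) | 2.27 |
| 0 | 2 | 42/42 = 100.0% (91.6–100.0) | 42/44 = 95.5% (84.5–99.4) | 4.55 |
| 2 | 1 | 41/43 = 95.3% (84.2–99.4) | 41/44 = 93.2% (81.3–98.6) | 2.17 |
| 2 | 2 | 40/42 = 95.2% (83.8–99.4) | 40/44 = 90.9% (78.3–97.5) | 4.33 |
| 4 | 1 | 39/43 = 90.7% (77.9–97.4) | 39/44 = 88.6% (75.4–96.2) | 2.06 |
| 4 | 2 | 38/42 = 90.5% (77.4–97.3) | 38/44 = 86.4% (72.6–94.8) | 4.11 |

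With d = 0 the two rates are identical.

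**Disease subsets (7.9.4), d = 1.** The approximate 25% minimum in 4.2 gives 0.25 × 44 = 11. Section 7.1.1.1 describes 18 subjects and then 5 more before a decision on starting the dissection arm. If all 44 are enrolled and none of those 23 has a dissection (an assumption for the first 18), up to 44 − 23 = 21 dissection subjects remain.

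| n | f | Evaluable-only | All enrolled | Gap, points |
|---|---|---|---|---|
| 21 | 0 | 20/20 = 100.0% | 20/21 = 95.2% | 4.8 |
| 21 | 1 | 19/20 = 95.0% | 19/21 = 90.5% | 4.5 |
| 21 | 2 | 18/20 = 90.0% | 18/21 = 85.7% | 4.3 |
| 11 | 0 | 10/10 = 100.0% | 10/11 = 90.9% | 9.1 |
| 11 | 1 | 9/10 = 90.0% | 9/11 = 81.8% | 8.2 |
| 11 | 2 | 8/10 = 80.0% | 8/11 = 72.7% | 7.3 |

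**Living subjects who cannot be assessed.** These differ, because the true outcome exists but was not seen. With N = 44, f = 2, d = 1 and one such subject, the evaluable-only rate is 40/42 = 95.2%. The all-enrolled rate is 40/44 = 90.9% if that subject is a failure and 41/44 = 93.2% if a success.

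**The case against.** A reader might infer that 7.1.2 and 7.1.3 contradict each other. The documents do not support that. Both start from all enrolled subjects, and 7.1.2 sits under protocol deviations, where it may mean only that subjects with deviations are not removed. Together they can mean that the set is all enrolled and each rate uses those with evaluable data, which matches denominators elsewhere in 7.9.3. That stands. But this reading is the one that drops the early death or conversion, and 7.9.2 does not say it was intended.

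A reader might also infer that ITT requires every unassessed subject to be a failure. Section 7.1.3 does not say so, and for living subjects that would be a worst-case imputation against the general rule in 7.4.

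The affected case is narrow. A technical failure fails by definition, observed endoleak or growth failures are retained, and Table 1 accepts 1-month images from day 15 to day 122. Deaths, conversions and imaging adequacy are tabulated (7.1.1.2), death and conversion rates are reported (7.9.3.1), and missing endpoint data are listed by subject (7.4). A careful reader could largely rebuild either rate. All of this stands, and it limits the harm without settling which rate is reported.

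Finally, a rule may exist in documents not available here. The readable protocol text is page headers only, and the SAP also points to table shell specifications and a reporting-conventions work instruction. The point therefore rests on the SAP alone.

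**Conclusion.** The point holds as an unresolved ambiguity with a predictable direction. The SAP does not fix the treatment-success denominator, and its most natural combined reading gives an evaluable-only rate that is too high whenever a technically successful implant is followed by death or conversion with no recorded failure and no evaluable image. The direction rests on treating such a subject as not successful. That is a reasonable estimand choice, but the SAP has not yet made it.

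The size is about 2 points per such subject at N = 44, with overlapping intervals. In a disease subset it is about 4 to 9 points as the size falls from 21 to 11. All counts are assumed, and if no such subject occurs there is no effect. No hypothesis test or success criterion is involved (SAP section 5). The change should be made because the rate is the primary effectiveness result, but it does not undermine the study.

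The dissection definitions are a separate matter. Section 4.3.2 asks for exclusion of the primary entry tear, while 7.9.3.3 defines false-lumen exclusion as "the exclusion of primary entry tear of dissection associated to the thrombosis of false lumen at the level of stent graft". Those passages need reconciling on their own.

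**What to change.** In 7.9.2, state that:

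1. The denominator is all enrolled subjects, as in 7.1.3.
2. Technical failure, non-implantation, and death or conversion before the 30-day imaging assessment count as not successful.
3. For subjects alive and unconverted whose exclusion or patency cannot be determined, the report gives their number, the evaluable-only rate, and the all-enrolled rate with them counted first as failures and then as successes. This group includes partly imaged subjects (Table 4 scenarios 6 and 7), such as those with only a non-contrast scan, which Table 2 does not accept for endoleak.

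Apply the same rules to the subset analyses in 7.9.4. No single imputation for living, unassessed subjects needs to be mandated, because the range shows what depends on them.

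The cost is a few sentences in the SAP and one or two table rows. The reported rate may be a few points lower. No data collection or clinical procedure changes.

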7.9.3. Additional Observations

7.9.3.1. Major Adverse Events and Major Clinical Events

The following observations will be assessed through clinical follow-up (office visit or phone contact):

- Major adverse events (MAEs) rates within 30 days of the initial or secondary procedures, including:
 - All-Cause Mortality
 - Myocardial Infarction
 - Paraplegia
 - Renal Failure
 - Stroke
 - Left Arm/Hand Ischemia
- Secondary endovascular procedures
- Rupture
- Conversion to surgery
- Surgical revascularization of the LSA
- **Paraparesis**

[figure not shown]
The rate of the above events will be calculated on the subject level, and for different reporting time points, the correspondent cutoff days will be used as shown in Table 3.

For each visit (or reporting time point), the event rate will be calculated as the proportion of the number of subjects with a certain event term over the number of evaluable subjects. The evaluable subjects at each reporting time point include all subjects who are enrolled by the snapshot date and

- 1) Had a clinical or safety event (e.g. MAE) within (on or before) the Reporting cutoff Days, or
- 2) Had a follow-up or days to last contact at or after the lower limit of the Reporting Window,

Revision [6.0]

Page 19 of 27

[figure not shown]
3) The Withdrawal Consent Date /Recorded Lost-to-Follow-up Date at or after the lower limit of the Reporting Window

'Days to MAE' (date of earliest MAE – date of index procedure) and 'Days to Last Contact' (date of last contact – date of index procedure) are usually used for the determination of the eligibility of the 'evaluable subject'. The last contact date will be calculated based on the information gathered from all available dates during the follow-ups.

Similarly, 'Days to any AEs' and 'evaluability' of any AEs will be determined with the same principle as described above.

- 1. For death, Use the date of death from the CEC form, if it is not available then use Date of Death from study exit form.
- 2. For withdrew ("Subject withdrew consent to participate in the study" or " Physician's decision to protect the welfare of the subject") or "Subject enrolled but not implanted, completed 1 month follow-up", use Date of Exit from study exit form.
- 3. For patients who exited study for LTF, complete FU, or other reason, use last known date in the study from:
 - 1) Adverse Event Form
 - (i) Date event started
 - (ii) Date of resolution
 - 2) Secondary Procedure Form: Date of secondary procedure
 - 3) Conversion to Open Repair Form: Date of Open Repair procedure
 - 4) Clinical follow-up Form (including unscheduled)
 - (i) Date physical exam performed
 - (ii) Date of Labs:
 - 5) Imaging follow-up Form: Date of diagnostic imaging (including unscheduled imaging)
 - 6) For patients who exited study with no follow-up, use last known date in the study from:
 - (i) Procedure Form: Date of procedure
 - (ii) Discharge Form: Date of discharge

Revision [6.0] Page 20 of 27

7) For Patients who did not exit study - Use last known date as above.

The 'Reporting Cutoff Days', 'Lower limit of the Reporting Window' and the correspondent visits are listed in Table 3:

Table 3. Reporting Window for MAE and Major Clinical Events

Visit	Reporting Cutoff Days	Lower Limit of the Reporting Window		
1-month	30 days post-index procedure	Days to last contact: 15 days post-index procedure		
6-month	183 days post-index procedure	Days to last contact: 153 days post-index procedure		
12-month	365 days post-index procedure	Days to last contact: 335 days post-index procedure		
24-month	730 days post-index procedure	Days to last contact: 674 days post-index procedure		
36-month	1095 days post-index procedure	Days to last contact: 1039 days post-index procedure		
48-month	1460 days post-index procedure	Days to last contact: 1404 days post-index procedure		
60-month	1825 days post-index procedure	Days to last contact: 1769 days post-index procedure		

In addition to the point estimate of the rate for each event at each time point, a two-sided 95% Confidence Interval will also be calculated for each correspondent point estimate using the exact binomial method.

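### The evaluable-subject rule in SAP 7.9.3.1 keeps every subject with an event but drops event-free subjects not yet due or lost early, so the MAE composite rate runs high, mainly at annual snapshots

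*SAP*

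**What the plan says.** The rule is in SAP 7.9.3.1. The rate at each reporting time point is "the proportion of the number of subjects with a certain event term over the number of evaluable subjects". The evaluable subjects "include all subjects who are enrolled by the snapshot date", with no minimum time since the index procedure, and must also meet one of three criteria:

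1. The event route: "Had a clinical or safety event (e.g. MAE) within (on or before) the Reporting cutoff Days, or"
2. The contact route: a visit or last contact dated no earlier than the Table 3 lower limit for that time point.
3. The exit route, for subjects who withdrew or were lost: "The Withdrawal Consent Date /Recorded Lost-to-Follow-up Date at or after the lower limit of the Reporting Window"

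The connector before the third criterion falls at a page break; I read it as another alternative. Table 3 gives the cutoffs and lower limits: 365 and 335 days at 12 months, 730 and 674 at 24 months, 1825 and 1769 at 60 months. Subjects still in the study take their last known date. Each rate gets a two-sided 95% exact binomial interval.

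The MAE item is worded "Major adverse events (MAEs) rates within 30 days of the initial or secondary procedures, including" followed by six components. The same section lists five further clinical event terms. For the MAE composite the qualifying date is the "date of earliest MAE".

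SAP 4.2 sends the data to FDA in annual progress reports and estimates 20 months of enrolment, with up to 44 subjects.

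**The concern.** Entry to the denominator depends on the outcome. Take two subjects implanted on the same day who have not reached Day 335 at the snapshot. The one with an early MAE enters the 12-month rate; the event-free one does not. A subject lost before the lower limit is treated the same way: kept with an event, dropped without one. A reported rate can then rise from one time point to the next with no new event.

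Long-term safety reporting is a stated purpose (SAP section 3), and SAP 4.2 says the data may support marketing applications. Intervals may be left out of annual reports (General Methodology), so the percentage may stand alone.

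**Working it through.** The SAP states no event rate to reproduce, so this is a check of the rule itself.

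**Inputs from the SAP.** n = 44, entry over 20 months (about 608 days), the Table 3 limits, exact binomial intervals. **Assumptions.** Uniform entry; all event and exit rates.

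**Direction.** Let D subjects be followed to the window and U not, with true risk F by the cutoff and observed early risk f among the U. The rule gives (D·F + U·f)/(D + U·f). The excess over F is U·f·(1 − F)/(D + U·f), which is positive whenever U and f are above zero. If all events are early this becomes p/(p + (1 − p)q), where q is the share of event-free subjects counted.

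**Small example.** Suppose 5 of 44 have an MAE by Day 30 and none later.
- True proportion at every later cutoff: 5/44 = 11.4% (exact 95% CI 3.8 to 24.6).
- Snapshot on Day 730 after first enrolment: (730 − 335)/608 = 65% have reached Day 335, so about 0.65 × 39 ≈ 25 event-free subjects count.
- Reported 12-month rate: 5/(5 + 25) = 16.7% (5.6 to 34.7).
- For p = 11.4% the formula gives 12.5% at q = 90%, 16.5% at 65% and 20.4% at 50%.

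**Expected value at 12% early risk, none later, no exits.**
- 12-month rate at 2 years: 0.12/(0.12 + 0.88 × 0.65) = 17.3%.
- 24-month rate at 3 years: q = (1095 − 674)/608 = 69%, so 0.12/(0.12 + 0.88 × 0.69) = 16.5%.

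**Simulation at annual snapshots (44 subjects, 20,000 replicates, no exits).**

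| Assumed risk | Rate and snapshot | Rule | True | Coverage |
|---|---|---|---|---|
| 12% by Day 30, none later | 12-month at 2 years | 17.3% | 12.0% | 89% |
| 12% by Day 30, none later | 24-month at 3 years | 16.4% | 12.0% | 91% |
| 5% by Day 30, none later | 12-month at 2 years | 7.5% | 5.0% | 94% |
| 20% by Day 30, none later | 12-month at 2 years | 27.8% | 20.0% | 86% |
| 12% by Day 30, then 2%/yr | 12-month at 2 years | 19.2% | 13.6% | 89% |
| 4%/yr, no early peak | 12-month at 2 years | 4.7% | 3.6% | 95–97% |
| 4%/yr, no early peak | 24-month at 3 years | 9.7% | 7.4% | 95–97% |

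**How long it lasts.** The last subject reaches the lower limit at Day 335 + 608 = 943 after first enrolment for the 12-month column, and at 674 + 608 = 1282 for the 24-month column.

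**Final report, where only early exits remain.** At 12 months the excess is 0.2 to 0.7 point. At 60 months, with 12% early risk:
- exits 2%/yr and other-cause deaths 2%/yr: 13.0% against 12.0% with no later events, 21.0% against 19.8% with 2%/yr later;
- exits 8%/yr and other-cause deaths 5%/yr: 16.1% against 12.1% (coverage 92%) and 23.9% against 19.4% (93%).

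**If criterion 1 means any clinical or safety event.** For a single term at the 12-month, 2-year snapshot, let 50%, 70% or 90% of subjects have some other early event. A term with 12% early risk then reads 14.3%, 13.3% or 12.4% (true 12.0%). A 4%/yr term reads 3.7%, 3.5% or 3.2% (true 3.6%).

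**The case against.** The strongest reply has four parts.

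- **Scope.** A reader might infer that every rate in 7.9.3.1 is inflated. The text does not support that. Criterion 1 names a clinical or safety event with MAE as an example. For a single term it does not say whether the qualifying event is that term, any MAE or any event. On the wide reading the inflation shrinks and can turn slightly negative. Nor do the documents say that MAEs cluster early: the MAE scope includes 30 days after a secondary procedure, which may come late. This stands, and it limits the claim to the composite and to same-term single rates.
- **Duration and visibility.** Each column's not-yet-due phase ends, and the accountability table in SAP 7.1.1.2 counts subjects not yet due at each visit. Attrition is also tabulated, and missing endpoint data and deaths are listed. This stands, but a count in another table does not correct the reported percentage.
- **Weight.** The study is descriptive, and exact intervals at these sizes are 21 to 30 points wide, so about 1 point in the final report is small. A reader might also infer that the 30-day primary safety result is affected; SAP 7.9.1 does not invoke this rule. Both limits stand.
- **The alternative in SAP 7.10.** For AEs other than MAEs, that section divides by subjects in the study at the start of the period, which does not depend on outcome. It is a per-period rate, however, and tends to run low at a snapshot when subjects have not finished the period. It is not a ready replacement.

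**Conclusion.** The concern holds for the MAE composite, and for a single term if criterion 1 means that same term. The upward direction follows from the rule and needs only that some subjects with early events are not yet due or leave before the lower limit. The size rests on assumed event and exit rates and uniform entry. It is about 4 to 5 points at annual snapshots for 12% risk concentrated by Day 30, and about 1 to 2 points for terms without an early peak. In the final report it is under 1 point at 12 months, about 1 point at 60 months with low attrition and about 4 with high attrition.

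One effect may pull the other way. Criterion 3 admits a recorded loss date, whereas the last-contact rule reads "For patients who exited study for LTF, complete FU, or other reason, use last known date in the study from" the study forms. If recorded dates are later than last contact, some subjects count as event-free for time not observed. The documents do not allow that to be sized.

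This is worth correcting because the figures go to FDA each year. It does not undermine a hypothesis test, since the study has none.

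**What to change.** 1. At each Table 3 time point report Kaplan-Meier for all-cause mortality. For the MAE composite and the other terms report cumulative incidence, with death outside the term's definition as a competing event. Keep the SAP's MAE scope, censor at last actual contact, and give matching 95% intervals (for example log-log). For a term with zero events, give an exact binomial upper bound on subjects with contact at or after the lower limit. In simulation this package averaged within 0.1 point of truth, with coverage 93.9% to 97.8%. It is not immune: if events are reported between visits but event-free time runs only to the last visit, it also reads high (worst case 9.5% against 7.5%; the present rule gave 11.9%).
2. If the proportions stay as a supplementary table, limit numerator and denominator to subjects whose index procedure was at least the lower-limit number of days before the snapshot, with or without an event. This removes the not-yet-due bias (11.8% against 12.0% in the 12-month case) but not the smaller bias from early loss.
3. In that table tie criterion 1 to the term analysed, state how deaths before the cutoff are handled, and reconcile criterion 3 with the last-known-date rule for subjects lost to follow-up.
4. Use the same estimator in the disease subsets already planned in SAP 7.9.4.

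The cost is SAP wording and a little programming on dates already collected. Figures will differ from earlier annual reports; the supplementary table can sit beside them.

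### SAP 7.9.3.1 lets any major event make a subject evaluable for every other event term, so unobserved follow-up counts as event-free in the long-term denominators

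*SAP*

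**What the plan says.** SAP section 7.9.3.1 covers the MAE terms together with secondary procedures, rupture, conversion, surgical LSA revascularization and paraparesis. The rate at each time point is the "number of subjects with a certain event term over the number of evaluable subjects".

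The denominator is defined once per time point: "The evaluable subjects at each reporting time point include all subjects who are enrolled by the snapshot date and" meet at least one of three criteria.

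- Criterion 1: the subject "Had a clinical or safety event (e.g. MAE) within (on or before) the Reporting cutoff Days".
- Criterion 2, joined to the first by an or: "Had a follow-up or days to last contact at or after the lower limit of the Reporting Window".
- Criterion 3: a consent-withdrawal or loss-to-follow-up date at or after the same lower limit.

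Days to MAE is counted from the index procedure to the "date of earliest MAE", whatever its type. That count and days to last contact are "usually used for the determination of the eligibility of the" evaluable subject. A further sentence extends the same principle to any AE.

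Table 3 sets the 60-month cutoff at Day 1825 and its lower limit at Day 1769. At 1 month the figures are Day 30 and Day 15. Each rate carries a two-sided 95% exact binomial interval.

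**The concern.** The numerator belongs to one event term; the denominator does not. An early MAE of one kind is enough to make a subject evaluable for all the others, at every later time point, with no contact required near that time point. The subject is then counted as free of events that nobody was in a position to observe.

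Two subjects with identical observation for rupture can be treated differently because one of them had an unrelated MI. Whatever its size, that is a flaw in the rule.

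The terms most exposed accrue over years: secondary procedures, rupture, conversion and LSA revascularization. The study is descriptive, so these rates and intervals are themselves the results. SAP sections 4.1 and 4.2 foresee the data being used for marketing applications.

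**Working it through.** **The rule applied to two subjects.** The SAP gives no rate, denominator or dropout figure for this point, so there is nothing to reproduce. Take two subjects who both withdraw on Day 60 (an assumed day). Subject A had a non-fatal MI on Day 3; subject B had no event.

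- A at 60 months: the MI precedes Day 1825, so criterion 1 is met. A counts as a non-event for rupture and conversion, although observed for 60/1825 = 3% of the interval.
- B at 60 months: no event, and last contact and withdrawal precede Day 1769. All three criteria fail and B is dropped.

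**Other sections of the same SAP.** Imaging rates (7.9.3.6) use subjects assessed for the particular event. The aneurysm exclusion endpoint (7.9.3.3) drops subjects who have no failure but lack a component. AEs other than MAEs (7.10) use subjects still in the study when the period begins. None of these lets an unrelated event make a subject evaluable.

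**Size of the dilution.** Let n be the subjects evaluable without the problem, d the further subjects who had an event of another term and left before the lower limit, and x the subjects with the term. As written the rate is x/(n+d); per term it is x/n. The ratio is n/(n+d).

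The counts below are assumptions, bounded only by the planned maximum of 44. Everyone with the term is taken to be among the n. Intervals are exact 95%.

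| n | d | x | As written | Per term | Relative reduction |
|---|---|---|---|---|---|
| 36 | 2 | 2 | 2/38 = 5.3% (0.6 to 17.7) | 2/36 = 5.6% (0.7 to 18.7) | 1 − 36/38 = 5% |
| 30 | 6 | 3 | 3/36 = 8.3% (1.8 to 22.5) | 3/30 = 10.0% (2.1 to 26.5) | 1 − 30/36 = 17% |
| 24 | 8 | 3 | 3/32 = 9.4% (2.0 to 25.0) | 3/24 = 12.5% (2.7 to 32.4) | 1 − 24/32 = 25% |
| 30 | 6 | 0 | 0/36 = 0% (upper limit 9.7) | 0/30 = 0% (upper limit 11.6) | none; only the limit moves |

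At 1 month only exits before Day 15 can add to d, so the effect there is small.

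**Net direction.** The rule also drops event-free exits and keeps subjects who had the term and then left, which pushes rates up. Suppose a true 5-year risk p = 10%, no deaths, and a share e of subjects leaving evenly over the five years, so that about half of a leaver's risk is observed.

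- Share seen to have the term: p(1 − e/2).
- Share evaluable with a per-term criterion 1: (1 − e) + e·p/2.
- As written, add q·e(1 − p/2), where q is the share of term-free leavers who had another qualifying event.

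For e = 20%: per term 0.09/0.81 = 11.1%. As written the rate runs from 11.1% (q = 0) to 0.09/1.00 = 9.0% (q = 1).

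For e = 35%: per term 0.0825/0.6675 = 12.4%. As written it runs from 12.4% to 0.0825/1.00 = 8.25%.

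The literal rule therefore falls on either side of the true 10%. It crosses at q = (0.90 − 0.81)/0.19 = 47%, and at the same 47% for e = 35%: (0.825 − 0.6675)/0.3325.

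**Early exits.** Take 24 followed and 8 leaving after about a tenth of the follow-up, all 8 with another event, and p = 10%. Expected subjects with the term: 24 × 0.10 + 8 × (1 − 0.9^0.1) = 2.484. As written: 2.484/32 = 7.8%. Per term: 2.484/(24 + 0.084) = 10.3%. The per-term rule is clearly better here. With exits spread evenly and q below 47%, it lies further from the truth than the literal rule.

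**The case against.** The best defence is that the text can be read per term. The day counts are only usually used, MAE is given as an example, the earliest-MAE date is correct for a composite MAE rate, and extending the principle to any AE could mean repeating it with each event's own onset. A careful programmer might do exactly that. This reading is possible but not written: the evaluable set is defined per time point, and no per-term date is given. What stands is that the SAP should say which reading applies.

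It is also fair that these are additional observations in a feasibility study with no hypothesis tests, and that 2/38 against 2/36 is a trivial shift inside an interval about 17 to 18 percentage points wide. That limits the importance without removing the flaw.

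Three stronger readings are tempting and are not supported:

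- A reader might infer that any AE satisfies criterion 1, so that nearly all 44 subjects count at every time point. The section concerns major events, and that reading would leave criteria 2 and 3 and the Table 3 lower limits with nothing to do.
- A reader might infer that the long-term rates are understated. The working shows that the net error can go either way.
- A reader might infer that bias disappears only if every subject with an early event is followed. The point estimate is also correct if the retained subjects truly never had the term, and the dilution is nil when nobody has it.

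**Conclusion.** The point holds as a defect in the denominator rule. On the plain wording of section 7.9.3.1, inclusion at later time points depends on an event unrelated to the one being reported, and unobserved time is credited as event-free. No other SAP section corrects this. The protocol text available for this review holds only page headers, so it could not be checked for a different definition.

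The dilution factor n/(n+d) is exact; its size rests wholly on assumed counts, because the documents give no follow-up losses. Keeping early deaths in every denominator is not part of the problem: their later status is known, and no further event can occur. The issue is withdrawal and loss to follow-up after a non-fatal event. What is at stake is the accuracy of descriptive rates and intervals, not type I error.

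**What to change.** - Determine evaluability separately for each event term. Criterion 1 becomes: had the term being reported on or before the cutoff day. A subject with only some other non-fatal event must qualify through criterion 2 or 3. The earliest-MAE date remains right for a composite MAE row.
- State explicitly that deaths before the cutoff stay in every denominator. Under a per-term criterion 1 an early death could otherwise fail all three criteria.
- For time points after 1 month, also report a per-term cumulative incidence estimate with death as a competing event and censoring at last contact. The new wording alone removes the dilution but leaves the upward bias, and can enlarge the net error.
- Reconcile the sentence extending the rule to any AE with the at-risk denominator in section 7.10.

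The cost is a few sentences in the SAP, a per-term denominator and one further estimate in the programs. Denominators will differ between rows of the same table and need a footnote. No new data are needed, since event, exit and last-contact dates are already collected.
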